Recruitment and consent are required since it is a prospective study. Patients will be identified for potential enrollment in this study from the lab schedules at Aurora St. Luke's Medical Center. The potential subjects medical record will be screened to determine eligibility. Patients found to be eligible will be considered for enrollment and may be contacted prior to the procedure to assess interest in participation.

VI. Specimen/Data Collection and Procedures

The source of data for this study will be the electronic medical record (Epic, Madison, WI). Only people included in this IRB will access the compiled data. Medical record information generated after the approval of this IRB will be collected up until the conclusion of the study.

VII. Risks, Protection & Benefits

Risks/adverse events as reported in the IFU – these complications may occur and/or be related to the procedure or the vascular closure:

- Allergic response
- Anemia
- Arterial stenosis/occlusion
- Arterio-venous fistula
- Bleeding from the puncture site
- Bruising/hematoma
- Death
- Device failure/malfunction/misplacement
- Device Entrapment
- Diminished pulses distal to closure site
- Hypotension/hypertension
- Edema
- Embolism
- Pulmonary Embolism
- Numbness
- Infection/sepsis
- Inflammatory response
- Intimal tear/dissection
- Ischemia distal to closure site
- Perforation of the vessel wall
- Nerve injury
- Pseudoaneurysm
- Retroperitoneal hematoma/bleeding
- Deep vein thrombosis
- Vascular injury
- Vasovagal episode
- Vasoconstriction/vasospasm
- Wound dehiscence
- Pain

• Thrombus formation

Risks of figure 8 suture method:

- Pain
- Pressure
- Hematoma
- Bleeding
- Vessel rupture
- Surgery

Benefits:

Depending on the closure strategy subjects may experience a decrease in bedrest time post procedure with potentially less complications.

Results of this study may also be generalizable to the larger healthcare community by informing standard of care guidelines for obtaining hemostasis and post procedure outcomes following the procedures studied in this protocol.

VIII. Adverse Event Reporting

Definitions

Adverse event: Any untoward medical occurrence, unintended disease or injury or untoward clinical signs in subjects, users, or other persons, whether or not related to the medical device.

Serious adverse event: Any adverse event that led to

- Death
- Life-threatening illness or injury
- Permanent impairment
- Prolonged hospitalization or change to inpatient status

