An interim monitoring plan to perform periodic checks of the data after the first 25 subjects are enrolled and then again after 75 subjects are enrolled will be reviewed by the Biostatistician or study team to determine data integrity, accuracy, and consistency with the study objectives/hypotheses as well as preliminary analysis.

X. Statistical Considerations

A convenient sample size of approximately 55 subjects in each of the two randomized groups (Perclose ProGlide SMC and figure 8 suture) was determined to allow for parametric statistical methods. Following interim analysis: O'Brien-Fleming method was selected to adjust the p-value for interim analysis and final analysis. It was also used to calculate the required sample size at each stage of analysis in order to achieve 80% power in the outcome. Final sample size required was determined at 101 subjects. A 10% +/- should be added, to bring the total enrollment to 110 subjects.

XI. Outcomes

Primary outcomes: time to achieve hemostasis (TTH) and time to ambulate (TTA)

Secondary outcomes: time to discharge (TTD)/length of stay, post procedure major bleeding, mortality due to vascular complications, minor bleeding, access site hematoma, vascular thrombosis, vascular dissection, pseudoaneurysm, or AV fistula.

TTH: The elapsed time between "device" removal and first observed and confirmed venous hemostasis.

TTA: The elapsed time between removal of the final Perclose ProGlide SMC device (treatment arm) or removal of the final sheath (control arm), and the ability of subjects to stand and ambulate 20 feet without evidence of venous re-bleeding from the femoral access sites.

TTD/LOS: The elapsed time between removal of the final sheath, and the ability of subjects to be discharged. Length of hospital stay.

Major bleeding: Bleeding associated with ≥ 2 g/dl drop in hemoglobin level requiring transfusion, bleeding that occurs at a critical site, or bleeding contributing to death.

Minor Bleeding: Any bleeding that does not meet the criteria for major bleeding.

XII. Regulatory Requirements

Approval from the Aurora Health Care IRB will be obtained to perform this study, which includes approval of all associated informed consent forms. All protocol modifications and corresponding informed consent forms will be submitted for review and approval prior to implementing.

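### Time to ambulation, a primary outcome, starts at a different event in each arm, so any gap between sheath removal and Perclose device removal enters the treatment comparison

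*Combined protocol and SAP*

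**What the plan says.** All three time intervals are defined in Section XI (Outcomes).

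- **Status of TTA.** "Primary outcomes: time to achieve hemostasis (TTH) and time to ambulate (TTA"). Section II gives the hypothesis that the closure device shortens time to hemostasis (TTH), TTA and time to discharge (TTD).
- **TTA start.** It differs by arm: "removal of the final Perclose ProGlide SMC device (treatment arm) or removal of the final sheath (control arm"). The end event, walking 20 feet without re-bleeding, is the same in both arms.
- **TTD start.** There is no arm split: "The elapsed time between removal of the final sheath, and the ability of subjects to be discharged".
- **TTH start.** "The elapsed time between 'device' removal and first observed and confirmed venous hemostasis". Section XI does not say what the word device covers in either arm.

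No section says that the two TTA start events coincide, gives their order or the time between them, or plans a TTA analysis from a common start. Section III refers to an attached Excel file of study variables, which is not part of the public document. Section VI says of the data: "The source of data for this study will be the electronic medical record (Epic, Madison, WI").

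**The concern.** A time-to-event outcome compares arms fairly when the clock starts at the same event in both. Here the assigned treatment decides which event starts it. Time spent between final sheath removal and final device removal is counted differently in the Perclose arm from the way it would be counted in the figure-8 arm. Randomization balances patients, but this offset comes from the definition and so survives it.

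What is at stake is how a TTA result can be read. If the difference favours Perclose, a reader cannot tell how much of it comes from the closure method and how much from the clock. If the offset runs the other way, a real benefit could be diluted.

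**Working it through.** **1. The algebra.** For a Perclose subject let g = (time of final device removal) − (time of final sheath removal). Then

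TTA as planned = TTA from final sheath removal − g.

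Control-arm TTA already starts at final sheath removal. Hence

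planned difference (Perclose − control) = common-start difference − mean of g in the Perclose arm.

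If g is positive, the planned clock flatters Perclose. If g is negative, it penalises Perclose. If g is zero, nothing changes. The documents do not give the sign or the size of g.

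**2. Inputs.**

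- From the plan: 101 subjects required and 80% power (Section X), 1:1 allocation (Section III), two-sided p < 0.048 at the final analysis (Section IX).
- Assumed, because the plan gives none: the size of the offset, the SD of TTA, a constant offset, a two-sample t-test. Interim looks are not modelled.

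The plan states no effect size or SD, so its figure of 101 cannot be rebuilt, and this point does not depend on it.

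**3. Rejection rate with no true difference.** With 50 and 51 subjects there are 99 degrees of freedom and the critical value is 2.002. The noncentrality is

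(offset / SD) / √(1/50 + 1/51) = 5.025 × offset / SD.

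Example: 5 minutes at an SD of 60 minutes gives 5.025 × 0.0833 = 0.419, and the noncentral t then rejects with probability 6.7%.

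| Assumed offset | SD 3 h | SD 2 h | SD 1 h |
|---|---|---|---|
| 0 min | 4.8% | 4.8% | 4.8% |
| 2 min | 4.8% | 4.9% | 5.1% |
| 5 min | 5.0% | 5.3% | 6.7% |
| 10 min | 5.7% | 6.7% | 12.8% |

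Only the ratio of offset to SD matters. Rejection reaches 10% at 0.135 SD, which is 24, 16 and 8 minutes at SDs of 3, 2 and 1 hours. If the SD were only 30 minutes, a 5-minute offset has the same ratio as 10 minutes at 1 hour, so 12.8%.

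**4. Loss of power if the offset opposes Perclose.** The effect giving 80% power under these inputs is 0.567 SD (back-calculated). Subtracting 5 minutes leaves 0.567 − 5/180 = 0.539, 0.567 − 5/120 = 0.525 and 0.567 − 5/60 = 0.483 SD. Power falls to 76%, 74% and 67%.

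**5. Skewed data.** Section IX allows non-parametric methods. In 20,000 simulated lognormal trials per setting, with a 5-minute offset and SDs of 3, 2 and 1 hours, the Mann-Whitney test rejects 5.1%, 5.7% and 7.5% of the time at a coefficient of variation of 0.5, and 5.5%, 6.8% and 12.2% at 1.0. The pattern is the same, and stronger with marked skew.

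**6. With one common start event** the offset is zero by construction, the nominal 4.8% is restored, and no sample size changes.

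**The case against.** The strongest defence is that the TTA text applies one rule to both arms: start when the last access or closure hardware leaves the vein. On that view the split is a choice of what to measure. The plan does not state this rationale, though, and TTD does not follow it. Even if it was intended, a reader would still need the common-start result to see how much the choice matters.

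A second defence is size. If TTA varies by 2 to 3 hours, an offset of a few minutes barely moves the error rate. This stands, and it limits how much weight the point can carry.

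A third is that redefining a primary outcome late has its own cost. Section X says "Following interim analysis: O'Brien-Fleming method was selected to adjust the p-value for interim analysis and final analysis", which reads as though an interim analysis has been done, and Section IX says that interim checks, including preliminary analysis, "will be reviewed by the Biostatistician or study team". This also stands. It argues for adding an analysis, and it leaves open which clock should lead.

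Three stronger readings are tempting, and the documents support none of them.

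- A reader might infer that the definition favours Perclose. That holds only if the device comes out after the sheath, and no section states the order.
- A reader might infer that TTH has the same split, since the TTA line could explain what device means there. That is not shown, and the study-variables file may settle it.
- A reader might infer that the TTD line proves final sheath removal to be the right clock for TTA. It shows only that a common event is available.

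**Conclusion.** The asymmetry is explicit in Section XI and affects a primary outcome. Following the plan as written puts any interval between sheath removal and device removal into the TTA contrast. That much is certain from the text. Whether the interval is material is not known: its direction and size cannot be derived from the documents, and every rate above rests on an assumed offset and SD. On those assumptions the effect is small if TTA varies by 2 to 3 hours and no longer negligible at 1 hour or less. It should be fixed because it is avoidable at low cost, not because a large bias has been demonstrated. TTH remains a query about the meaning of one word.

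**What to change.** 1. Record the final sheath-removal time in both arms. Add to Section XI a TTA analysis starting at that event in both arms, reported alongside the device-based clock. Require the two to agree before concluding on TTA, and say in advance what agreement means (for instance, same direction and both below 0.048).
2. Which clock leads is for the sponsor to decide. If the common start becomes the primary definition, make the change by a dated amendment, decided without reference to by-arm results, and disclose who decided and what interim results they had seen. Section XII already provides the route: "All protocol modifications and corresponding informed consent forms will be submitted for review and approval prior to implementing".
3. Report by arm how many patients lack a usable sheath-removal time.
4. For TTH, state what device removal means in each arm. Apply the same common-start analysis only if the meaning differs by arm.

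**Cost.** One extra analysis and some added wording. Control-arm TTA is unchanged, so only the Perclose arm (about 55 of 110 planned subjects) needs a second calculation. TTD already requires the sheath-removal time in every subject, so no new variable should be needed. Some times taken retrospectively from the medical record may be missing or imprecise. Requiring agreement can cost some power. If the primary definition changes, it changes after an apparent interim look, which is why both clocks must stay in the report.
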